### **Headache Characteristics (structured interview)**

How many days per month (28 days) with headache of any kind/severity: \_\_\_\_\_ / 28 days

How many days per month (28 days) with complete headache freedom: \_\_\_\_\_ / 28 days

How long do headaches last if untreated/inadequately treated: hours

How long do headaches last if successfully treated: hours

Where are they usually located (circle all that apply):

Right                    Left                    Front                    Back                    Side

Unilateral location:                    Yes                    No

Quality (circle all that apply):

Pulsating/Throbbing                    Pressure/Aching                    Stabbing                    Burning

Intensity:  
Mild                    Moderate                    Severe

Average on 0 (no pain) to 10 (most severe pain) scale: /10

Maximum on 0 (no pain) to 10 (most severe pain) scale: /10

Headaches worse with physical activity:                    Yes                    No

Headache worse with mental activity:	Yes	No
Nausea:	Yes	No
Vomiting:	Yes	No
Sensitivity to light:	Yes	No
Sensitivity to sound:	Yes	No
Conjunctival injection:	Yes	No
Tearing:	Yes	No
Nasal congestion/rhinorrhea:	Yes	No
Eyelid drooping:	Yes	No
Auras with headaches:	Yes	No
Visual:	Yes	No
Sensory:	Yes	No
Motor:	Yes	No
Dysphasia:	Yes	No
Other:	Yes	No

Percentage of headaches you experience auras: \_\_\_\_\_

When was your first headache (month and year): \_\_\_\_\_

Family history of migraine: Yes No  
 If yes, who:

### Medications

Currently taking medications to prevent headaches: Yes No

If yes, list medications:

---

---

---

---

---

---

Days per month (28 days) taking abortive medications: \_\_\_\_\_ days

Medication Name

---

---

---

---

Days/month taking

---

---

---

---

### **Personal Medical History**

#### **Current Medical Conditions**

1. \_\_\_\_\_
2. \_\_\_\_\_
3. \_\_\_\_\_
4. \_\_\_\_\_
5. \_\_\_\_\_
6. \_\_\_\_\_
7. \_\_\_\_\_
8. \_\_\_\_\_
9. \_\_\_\_\_
10. \_\_\_\_\_

11. \_\_\_\_\_

12. \_\_\_\_\_

13. \_\_\_\_\_

14. \_\_\_\_\_

**Past Medical Conditions/ Surgeries**

1. \_\_\_\_\_

2. \_\_\_\_\_

3. \_\_\_\_\_

4. \_\_\_\_\_

5. \_\_\_\_\_

6. \_\_\_\_\_

7. \_\_\_\_\_

8. \_\_\_\_\_

9. \_\_\_\_\_

10. \_\_\_\_\_

11. \_\_\_\_\_

12. \_\_\_\_\_

13. \_\_\_\_\_

14. \_\_\_\_\_

**Current Medications and Other Treatments**

Medication/Treatment Name	Dose	Frequency	Start Date	Stop Date
1. _____	_____	_____	_____	_____
2. _____	_____	_____	_____	_____
3. _____	_____	_____	_____	_____
4. _____	_____	_____	_____	_____
5. _____	_____	_____	_____	_____
6. _____	_____	_____	_____	_____
7. _____	_____	_____	_____	_____
8. _____	_____	_____	_____	_____
9. _____	_____	_____	_____	_____
10. _____	_____	_____	_____	_____
11. _____	_____	_____	_____	_____

12. \_\_\_\_\_

13. \_\_\_\_\_

14. \_\_\_\_\_

**Prior Migraine Treatments**

Medication/Treatment Name

Dose

Frequency

Months of Use

1. \_\_\_\_\_

2. \_\_\_\_\_

3. \_\_\_\_\_

4. \_\_\_\_\_

5. \_\_\_\_\_

6. \_\_\_\_\_

7. \_\_\_\_\_

8. \_\_\_\_\_

9. \_\_\_\_\_

10. \_\_\_\_\_

11. \_\_\_\_\_

12. \_\_\_\_\_

13. \_\_\_\_\_

14. \_\_\_\_\_

**Allodynia Symptom Checklist 12 – Ictal**

**How often do you experience increased pain or an unpleasant sensation on your skin during your most severe type of headache when you engage in each of the following?**

	Does not apply to me	Never	Rarely	Less than half the time	Half the time or more
Combing your hair					
Pulling your hair back (e.g., ponytail)					
Shaving your face					
Wearing eyeglasses					
Wearing contact lenses					
Wearing a necklace					
Wearing earrings					
Wearing tight clothing					
Taking a shower (when shower water hits your face)					
Resting your face or head on a pillow					
Exposure to heat					

(e.g., cooking, washing your face with hot water)					
Exposure to cold (e.g., using an ice pack, washing your face with cold water)					

### Allodynia Symptom Checklist 12 – Interictal

*How often do you experience increased pain or an unpleasant sensation on your skin when you do not have a severe headache when you engage in each of the following?*

	Does not apply to me	Never	Rarely	Less than half the time	Half the time or more
Combing your hair					
Pulling your hair back (e.g., ponytail)					
Shaving your face					
Wearing eyeglasses					
Wearing contact lenses					
Wearing a necklace					
Wearing earrings					
Wearing tight clothing					
Taking a shower (when shower water hits your face)					
Resting your face or head on a pillow					
Exposure to heat					

(e.g., cooking, washing your face with hot water)					
Exposure to cold (e.g., using an ice pack, washing your face with cold water)					

### **Beck Depression Inventory**

***Instructions: Choose one statement from among the group of four statements in each question that best describes how you have been feeling during the past few days. Circle the number beside your choice.***

- 1) 0 = I do not feel sad.  
1 = I feel sad.  
2 = I am sad all the time and I can't snap out of it.  
3 = I am so sad or unhappy that I can't stand it.
- 2) 0 = I am not particularly discouraged about the future.  
1 = I feel discouraged about the future.  
2 = I feel I have nothing to look forward to.  
3 = I feel that the future is hopeless and that things cannot improve.
- 3) 0 = I do not feel like a failure.  
1 = I feel I have failed more than the average person.  
2 = As I look back on my life, all I can see is a lot of failure.  
3 = I feel I am a complete failure as a person.
- 4) 0 = I get as much satisfaction out of things as I used to.  
1 = I don't enjoy things the way I used to.  
2 = I don't get any real satisfaction out of anything anymore.  
3 = I am dissatisfied or bored by everything.
- 5) 0 = I don't feel particularly guilty.  
1 = I feel guilty a good part of the time.  
2 = I feel quite guilty most of the time.  
3 = I feel guilty all of the time.
- 6) 0 = I don't feel I am being punished.  
1 = I feel I may be punished.  
2 = I expect to be punished.

3 = I feel I am being punished.

7) 0 = I don't feel disappointed in myself.  
1 = I am disappointed in myself.  
2 = I am disgusted with myself.  
3 = I hate myself.

8) 0 = I don't feel I am any worse than anybody else.  
1 = I am critical of myself for my weaknesses or mistakes.  
2 = I blame myself all the time for my faults.  
3 = I blame myself for everything bad that happens.

9) 0 = I don't have any thoughts of killing myself.  
1 = I have thoughts of killing myself, but would not carry them out.  
2 = I would like to kill myself.  
3 = I would kill myself if I had the chance.

10) 0 = I don't cry any more than usual.  
1 = I cry more now than I used to.  
2 = I cry all the time now.  
3 = I used to be able to cry, but now I can't cry even though I want to.

11) 0 = I am no more irritated by things than I ever am.  
1 = I am slightly more irritated now than usual.  
2 = I am quite annoyed or irritated a good deal of the time.  
3 = I feel irritated all the time now.

12) 0 = I have not lost interest in other people.  
1 = I am less interested in people than I used to be.  
2 = I have lost most of my interest in other people.  
3 = I have lost all of my interest in other people.

13) 0 = I make decisions about as well as I ever could.  
1 = I put off making decisions more than I used to.  
2 = I have greater difficulty in making decisions than before.  
3 = I can't make decisions at all anymore.

14) 0 = I don't feel that I look any worse than I used to.  
1 = I am worried that I am looking old or unattractive.  
2 = I feel that there are permanent changes in my appearance that make me look unattractive.  
3 = I believe that I look ugly.

15) 0 = I can work about as well as before.  
1 = It takes an extra effort to get started at doing something.  
2 = I have to push myself very hard to do anything.

3 = I can't do any work at all.

16) 0 = I can sleep as well as usual.  
1 = I don't sleep as well as I used to.  
2 = I wake up 1-2 hours earlier than usual and find it hard to get back to sleep.  
3 = I wake up several hours earlier than I used to and cannot get back to sleep.

17) 0 = I don't get more tired than usual.  
1 = I get tired more easily than I used to.  
2 = I get tired from doing almost anything.  
3 = I am too tired to do anything.

18) 0 = My appetite is no worse than usual.  
1 = My appetite is not as good as it used to be.  
2 = My appetite is much worse now.  
3 = I have no appetite at all anymore.

19) 0 = I haven't lost much weight, if any, lately.  
1 = I have lost more than five pounds.  
2 = I have lost more than ten pounds.  
3 = I have lost more than fifteen pounds.  
(Score 0 if you have been purposely trying to lose weight.)

20) 0 = I am no more worried about my health than usual.  
1 = I am worried about physical problems such as aches and pains, or upset stomach, or constipation.  
2 = I am very worried about physical problems, and it's hard to think of much else.  
3 = I am so worried about my physical problems that I cannot think about anything else.

21) 0 = I have not noticed any recent change in my interest in sex.  
1 = I am less interested in sex than I used to be.  
2 = I am much less interested in sex now.  
3 = I have lost interest in sex completely.

### **State Anxiety**

**Directions:** A number of statements which people have used to describe themselves are given below. Read each statement and then circle the appropriate number to the right of the statement to indicate how you feel *right* now that is, *at this moment*. There are no right or wrong answers. Do not spend too much time on any one statement but give the answer which seems to describe your present feelings best.

	Not at all	Somewhat	Moderately so	Very much so
1. I feel calm	1	2	3	4
2. I feel secure	1	2	3	4
3. I am tense	1	2	3	4
4. I feel strained	1	2	3	4
5. I feel at ease	1	2	3	4
6. I feel upset	1	2	3	4
7. I am presently worrying over possible misfortunes	1	2	3	4
8. I feel satisfied	1	2	3	4
9. I feel frightened	1	2	3	4
10. I feel comfortable	1	2	3	4
11. I feel self-confident	1	2	3	4
12. I feel nervous	1	2	3	4
13. I am jittery	1	2	3	4
14. I feel indecisive	1	2	3	4
15. I am relaxed	1	2	3	4
16. I feel content	1	2	3	4
17. I am worried	1	2	3	4

18. I feel confused	1	2	3	4
19. I feel steady	1	2	3	4
20. I feel pleasant	1	2	3	4

### Trait Anxiety

**Directions:** A number of statements which people have used to describe themselves are given below. Read each statement and then circle the appropriate number to the right of the statement to indicate how you *generally* feel. There are no right or wrong answers. Do not spend too much time on any one statement but give the answer which seems to describe how you generally feel.

	Not at all	Somewhat	Moderately so	Very much so
21. I feel pleasant	1	2	3	4
22. I feel nervous and restless	1	2	3	4
23. I feel satisfied with myself	1	2	3	4
24. I wish I could be as happy as others seem to be	1	2	3	4
25. I feel like a failure	1	2	3	4
26. I feel rested	1	2	3	4
27. I am “calm, cool, and collected”	1	2	3	4
28. I feel that difficulties are piling up so that I cannot overcome them	1	2	3	4
29. I worry too much over something that really doesn’t matter	1	2	3	4
30. I am happy	1	2	3	4
31. I have disturbing thoughts	1	2	3	4
32. I lack self-confidence	1	2	3	4
33. I feel secure	1	2	3	4
34. I make decisions easily	1	2	3	4
35. I feel inadequate	1	2	3	4
36. I am content	1	2	3	4

37. Some unimportant thought runs through my mind and bothers me	1	2	3	4
38. I take disappointments so keenly that I can't put them out of my mind	1	2	3	4
39. I am a steady person	1	2	3	4
40. I get in a state of tension or turmoil as I think over my recent concerns and interests	1	2	3	4

### Migraine Disability Assessment (MIDAS)

*Instructions: Please answer the following questions about all your headaches over the last 3 months. Write your answer in the box next to each question. Write zero if you did not do the activity in the last 3 months.*

1) On how many days in the last 3 months did you miss work or school because of your headaches? (If you do not attend work or school enter zero in the box.)	____ Days
2) How many days in the last 3 months was your productivity at work or school reduced by half or more because of your headaches? (Do not include days you counted in question 1 where you missed work or school. If you do not attend school or work enter zero in the box.)	____ Days
3) On how many days in the last 3 months did you not do household work because of your headaches?	____ Days
4) How many days in the last 3 months was your productivity in household work reduced by half or more because of your headaches? (Do not include days counted in question 3, where you did not do household work.)	____ Days
5) On how many days in the last 3 months did you miss family, social, or leisure activities because of your headaches?	____ Days
(Questions 1-5)	Total
A) On how many days in the last 3 months did you have a headache? (If headache lasted more than 1 day, count each day.)	____ Days
B) On a scale of 0-10, on average, how painful were these headaches? (Where 0=no pain at all, and 10=pain which is as bad as it can be.)	____ 0-10

### **Migraine Functional Impact Questionnaire (MFIQ)**

- The following questions are about your ability to function in the **past 7 days**.
- We would like to understand how a **migraine** affects your **day-to-day activities**.
- Symptoms of migraine can include headache pain, nausea, vomiting, or sensitivity to light or noise.
- We want you to think about the symptoms that **you** experience and how they impact **your** day-to-day activities.
- Please answer all questions by selecting the one option that best describes your experience.

1. In the past 7 days, how often did a migraine limit your ability to **move your head**?

Never  
Rarely  
Sometimes  
Often  
Always

2. In the past 7 days, how often did a migraine limit your ability to **move your body**? (For example, standing up, walking, bending)

Never  
Rarely  
Sometimes  
Often  
Always

3. In the past 7 days, how often did a migraine **limit your usual activities that required physical effort**?

Does not apply; do not usually do activities that require physical effort  
Never  
Rarely

Sometimes  
Often  
Always

4. In the past 7 days, how often did you **feel that you needed to rest or lie down** during the day because of your migraine?

Never  
Rarely  
Sometimes  
Often  
Always

5. In the past 7 days, how often did you **feel too tired to do things** because of your migraine?

Never  
Rarely  
Sometimes  
Often  
Always

6. In the past 7 days, how difficult was it **to get yourself ready for the day**?

Not difficult  
A little difficult  
Moderately difficult  
Very difficult  
Extremely difficult

7. In the past 7 days, how often did you have difficulty completing **specific personal grooming activities**? (For example, brushing hair, shaving, applying make-up)

Never  
Rarely  
Sometimes  
Often  
Always

8. In the past 7 days, how often did a migraine **affect your daily routine or schedule?**

Never  
Rarely  
Sometimes  
Often  
Always

9. In the past 7 days, how often did you have **to change your plans** because of a migraine?

Never  
Rarely  
Sometimes  
Often  
Always

10. In the past 7 days, how difficult was it **to do your usual chores at home?**

Not difficult  
A little difficult  
Moderately difficult  
Very difficult  
Extremely difficult

11. In the past 7 days, how much did a migraine limit your ability **to do your usual chores outside the home?** (For example, shopping or running errands)

Not at all  
Slightly  
Moderately  
Very Much  
Extremely

12. In the past 7 days, how much did a migraine affect your **ability to do your usual work or study-related activities?**

Does not apply; I have not worked\* or studied at all during the past week for reasons unrelated to the disorder. \*Work includes paid or unpaid work.  
Not at all  
Slightly  
Moderately

Very Much  
Extremely

13. In the past 7 days, how much did a migraine affect your **ability to take care of your family?**

Does not apply; I do not live with family.  
Not at all  
Slightly  
Moderately  
Very Much  
Extremely

14. In the past 7 days, how difficult was it for you **to do activities that required you to concentrate?**

Not difficult  
A little difficult  
Moderately difficult  
Very difficult  
Extremely difficult

15. In the past 7 days, how difficult was it **to do activities in the presence of loud noises, strong smells, or bright lights?**

Does not apply; I do not need to do activities in the presence of loud noises, strong smells, or bright lights.  
Not difficult  
A little difficult  
Moderately difficult  
Very difficult  
Extremely difficult

16. In the past 7 days, how much did a migraine **affect your usual activities?**

Not at all  
Slightly  
Moderately  
Very Much  
Extremely

17. In the past 7 days, how much did a migraine affect your **usual social interactions?** (For example, with family, friends, or coworkers)

Not at all  
Slightly

Moderately  
Very Much  
Extremely

18. In the past 7 days, how often did you **avoid being around other people** because of a migraine?

Never  
Rarely  
Sometimes  
Often  
Always

19. In the past 7 days, how much did you have **to limit your social activities** because of a migraine?

Not at all  
Slightly  
Moderately  
Very Much  
Extremely

20. In the past 7 days, how often did a migraine **interfere with your relationship** with your partner or spouse?

Does not apply; do not have a partner or spouse  
Never  
Rarely  
Sometimes  
Often  
Always

21. In the past 7 days, how often did a migraine **limit your usual leisure activities**?

Never  
Rarely  
Sometimes

Often  
Always

22. In the past 7 days, how **frustrated** did you feel about being **unable to do what you needed to do** because of a migraine?

Not at all  
Slightly  
Moderately  
Very Much  
Extremely

23. In the past 7 days, how often did you **worry about your migraines**?

Never  
Rarely  
Sometimes  
Often  
Always

24. In the past 7 days, how often did you **feel like a burden on others** because of a migraine?

Never  
Rarely  
Sometimes  
Often  
Always

25. In the past 7 days, how often did you feel you **lacked control of your life** because of a migraine?

Never  
Rarely  
Sometimes  
Often  
Always

26. In the past 7 days, how **disappointed** did you feel about having a migraine?

Not at all  
Slightly  
Moderately  
Very Much  
Extremely

## **Migraine Scog**

In this section we want to understand whether your headaches affect your cognitive abilities while you experience a headache. We will provide you with a number of statements describing difficulties that you may face during a headache. We will ask you to indicate to what extent you experience these difficulties. The information you provide us with will inform how we approach your care and how well can deliver care to you.

### **During your Headaches...**

Do you feel confused?

- 2: Often
- 1: Sometimes
- 0: No

Do you have trouble performing tasks at your normal speed?

- 2: Often
- 1: Sometimes
- 0: No

Is it difficult to follow a route or path (driving or walking)?

- 2: Often
- 1: Sometimes
- 0: No

Do you have trouble thinking?

- 2: Often
- 1: Sometimes
- 0: No

Do you have trouble maintaining a line of thought?

- 2: Often
- 1: Sometimes
- 0: No

Is it difficult to understand words spoken to you?

2: Often

1: Sometimes

0: No

Is it difficult to organize a sentence or a conversation?

2: Often

1: Sometimes

0: No

Do you have trouble speaking out other people's names?

2: Often

1: Sometimes

0: No

Is it difficult to remember the correct name of objects?

2: Often

1: Sometimes

0: No

### **N-Back Task**

	Trial 1	Trial 2	Trial 3
--	----------------	----------------	----------------

Sum of Hits: \_\_\_\_\_

\_\_\_\_\_

\_\_\_\_\_

Sum of False Alarms: \_\_\_\_\_

\_\_\_\_\_

\_\_\_\_\_

Sum of Misses: \_\_\_\_\_

\_\_\_\_\_

\_\_\_\_\_

Sum of Correct Rejections: \_\_\_\_\_

\_\_\_\_\_

\_\_\_\_\_

Sum of total Hits across all Trials: \_\_\_\_\_

Sum of total False Alarms across all Trials: \_\_\_\_\_

Proportion of (total Hits – total FA) /number of Trials: \_\_\_\_\_

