## **Summary**

Compared to healthy people without migraine, migraine is associated with alterations in brain structure and function. This is a prospective, longitudinal, open-label study that will investigate brain magnetic resonance imaging changes amongst individuals with migraine following treatment with erenumab.

The Specific Aims of this study are to:

- 1. Identify changes in brain function and structure that correlate with response to erenumab.**
- 2. Develop models using imaging data to predict which patients will respond to erenumab.**  
Pre-treatment and early post-treatment imaging data will be used separately for predictive modeling.

The study will include 50 subjects with migraine aged 18-65 years who have 6-25 migraine days per month at baseline. Following a 4-week run-in phase, subjects will be treated twice with once monthly subcutaneous injections of erenumab 140 mg. Questionnaires, structured interviews, cognitive tests, quantitative sensory testing and brain imaging will be performed prior to and following erenumab treatment. These data will be collected at early time points after the first treatment as well as at eight weeks following the first treatment to allow for identification of early and late effects of erenumab on clinical, physiologic, and imaging outcomes and to determine if early physiologic and imaging outcomes predict clinical outcomes at eight weeks. Physiologic and imaging data will be compared to already collected data from healthy controls so as to interpret changes that are seen following treatment with erenumab.

The primary hypothesis is that improvements in migraine patterns associated with erenumab treatment will be associated with “normalization” of brain function. Secondarily, it is hypothesized that improvements in migraine patterns associated with erenumab treatment will be associated with “normalization” of brain structure, pain thresholds, and cognitive performance. Finally, it is hypothesized that exploratory analyses will demonstrate that there are early changes in brain function following the first treatment with erenumab and that these early changes will be predictive of longer-term clinical responsiveness to erenumab.

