### N-Back Task

For purposes of test standardization and data interpretation, all subjects will complete the computer-based version of the n-back task on one of two MacBook laptops. The software for the n-back task will be downloaded on the laptops and subject task performance will be automatically calculated and summarized- thus eliminating testing bias.

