#### Analysis Plans

*Specific Aim #1 (i.e. identify changes in brain structure and function that correlate with response to erenumab):* Pre-treatment and post-treatment MRI data will be used for within and between subject

comparisons. Within subject analyses will compare baseline brain activation and perfusion patterns and functional connectivity patterns pre-treatment to post-treatment. Between subject group analyses will compare post-treatment MRI data in erenumab responders to non-responders.

Similar comparisons will be made for pre- and post-treatment pain thresholds (i.e. results of quantitative sensory testing) and cognitive testing.

So as to help with the interpretation of differences between responders and non-responders, MRI data from erenumab-treated patients will be compared to healthy non-migraine control data that we have already collected during the conduction of previous studies, when available (although we have plenty of data for the majority of analyses, we have limited ASL data and no n-back data from healthy controls). Differences in brain structure and function of migraine patients prior to erenumab treatment compared to healthy controls will be identified. Results of this analysis will determine alterations of brain structure and functions in migraine patients compared to healthy controls. Areas where migraine patients show altered structure and function will be used as regions of interest (ROIs) to assess the longitudinal, within-group changes of erenumab responders and non-responders.

Although multiple analyses are planned using functional, structural, and perfusion data, the primary analysis for specific aim #1 will be the comparison of pre-treatment pain-induced regional activation strength vs. post-treatment pain-induced regional activation strength in erenumab responders and separately in erenumab non-responders.

Post-treatment changes in other measures of brain function as well as measures of brain perfusion, brain structure, cutaneous pain thresholds and cognitive function in those responding to erenumab and in those not responding will be explored.

Two-tailed T-Tests or Mann-Whitney U tests will be used to perform group comparisons on demographic and cognitive measures and on pain threshold data. Neuroimaging data will be analyzed using general linear model designs. Within-group changes on cognitive measures, sensory testing and neuroimaging data will be assessed by applying a general linear mixed model design.

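### The only n-back score the plan defines subtracts raw false-alarm counts from raw hit counts, so it is not a proportion, usually has no fixed chance level, and mixes memory with willingness to press

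*Combined protocol and SAP*

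**What the plan says.** The N-Back Task form (Appendix – Case Report Forms) has columns for Trials 1, 2 and 3. Each column takes sums of hits, false alarms, misses and correct rejections (for example "Sum of Correct Rejections"). Two grand totals follow, "Sum of total Hits across all Trials" and "Sum of total False Alarms across all Trials", and then the single derived score, "Proportion of (total Hits – total FA) /number of Trials". Misses and correct rejections are neither totalled nor used in it.

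The N-Back Task section of the Methods names no index. It says that "subject task performance will be automatically calculated and summarized- thus eliminating testing bias".

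The Summary makes cognition part of a secondary hypothesis about "normalization” of brain structure, pain thresholds, and cognitive performance". Table 1 places cognitive testing at baseline, week 2 and week 8. Analysis Plans, Specific Aim #1, covers the data in general terms: "Two-tailed T-Tests or Mann-Whitney U tests will be used to perform group comparisons on demographic and cognitive measures", and "Within-group changes on cognitive measures, sensory testing and neuroimaging data will be assessed by applying a general linear mixed model design". It does not say which n-back quantity is a cognitive measure. It adds that no n-back data exist for healthy controls.

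**The concern.** An n-back record holds two kinds of information: how well the participant tells targets from non-targets, and how readily the participant presses. Separating them requires hits as a share of targets and false alarms as a share of non-targets. The form's score does neither. One false alarm cancels one hit, however many opportunities there were for each.

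The study is open-label with repeated testing, no concurrent untreated group and no control n-back data. If participants become more or less cautious between visits, nothing in the design would reveal it, so the score has to. Otherwise a change in response style could be reported as better or worse cognition in responders or non-responders.

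**Working it through.** The plan gives no numerical n-back figure to reproduce, so the check is of the formula.

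**Inputs.** From the form: raw counts and three Trial columns. From the Sample Size section: 21 patients per response group. Assumed, because the documents do not give them: 20 stimuli per Trial, hence 60 in all, and a target share between 20% and 50%. Write T for targets, N for non-targets, h for hit rate and f for false-alarm rate. The score is (T·h − N·f)/K, with K = 3 if Trials means the columns, or K = 60 if it means stimuli.

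**Is it a proportion?** A perfect record (h = 1, f = 0) scores T/K.

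| Target share | T / N | Perfect, K = 3 | Perfect, K = 60 | Always pressing, K = 3 |
|---|---|---|---|---|
| 25% | 15 / 45 | 5.0 | 0.25 | (15 − 45)/3 = −10.0 |
| 33% | 20 / 40 | 6.7 | 0.33 | (20 − 40)/3 = −6.7 |
| 50% | 30 / 30 | 10.0 | 0.50 | 0 |

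Under neither reading is 1 the maximum. The divisor only rescales the score.

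**Is there a chance level?** With no discrimination h = f = p, and the expected score is p(T − N)/3. This runs from 0 (never pressing) to the last column of the table (always pressing). It is fixed only when T = N. This step is algebra; only its size needs the target share.

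**Does the score move when ability is fixed?** In the equal-variance signal-detection model h = Φ(d′/2 − c) and f = Φ(−d′/2 − c), where a larger criterion c means more caution. Take d′ = 1.31 and move c from 0.2 to 0.7. Then h goes from 0.675 to 0.482, f from 0.196 to 0.088, and h − f from 0.479 to 0.394. The form's score (K = 3) changes as follows:
- 20% targets (12/48): −0.44 to +0.52
- 30% targets (18/42): 1.30 to 1.66
- 50% targets (30/30): 4.79 to 3.94

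The same behaviour looks like improvement or decline depending on the target share. The size also depends on ability: at d′ = 1.8 and 30% targets, the same shift moves the score only from 2.65 to 2.71.

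**How often would this give a false finding?** Paired t-tests with n = 21 and 4,000 runs; d′ mean 1.8, SD 0.5; c mean 0.2, SD 0.3; visit-to-visit SD 0.15 on each; no change in mean d′. All indices reject at about 5% when there is no shift. With a mean shift of 0.4 in c:

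| Target share | Form's score | h − f | d′ |
|---|---|---|---|
| 20% | 43% (as improvement) | 24% | about 5% |
| 30% | 9% | 30% | about 5% |
| 33% | 5% | 32% | about 5% |
| 40% | 9% | 34% | about 5% |
| 50% | 36% (as worsening) | 36% | about 6% |

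Halving the shift to 0.2 brings the form's score to about 20% at 20% targets, about 10% at 50%, and 5–8% in between.

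**Is d′ always the steadier index?** No. In a guessing model with true detection 0.7 and guess rate g, h = 0.7 + 0.3g and f = 0.3g. Raising g from 0.1 to 0.3 takes (h, f) from (0.73, 0.03) to (0.79, 0.09). Then h − f stays at 0.70, but d′ falls from 2.49 to 2.15, or 14%, with ability unchanged.

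**The case against.** Several counter-arguments have force.

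- **Nothing says this score is the endpoint.** This is correct. A reader might infer that the cognitive analysis is already committed to a flawed measure. The documents do not support that: Analysis Plans refers only to cognitive measures, and the counts needed for other indices are on the form. What stands is that this is the only n-back score defined anywhere.
- **The missing division is not the whole explanation.** Also correct. At 50% targets the form's score is proportional to h − f, yet it still rejects 36% of the time. At 30–40% targets, h − f alone does worse than the count score under this shift. It would be wrong to infer that converting to rates is enough.
- **The advantage of d′ is built into the signal-detection simulation.** Correct, as the guessing model shows. It would be wrong to infer that d′ is bias-free.
- **The assumed shift is large and undocumented.** A shift of 0.4 is 0.4/0.3 = 1.33 of the assumed between-person SDs of the criterion, in one direction across the group. No section gives a reason to expect it. The percentages are illustrations, not forecasts.
- **The Methods claim about testing bias.** A reader might take the form's score to contradict it. The sentence most naturally concerns administration and scorer bias, which automation does address, so there is no contradiction.
- **The stakes are low.** Cognition is explored, pain-induced activation is primary, and without control n-back data no scoring rule could show a return to normal performance.

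**Conclusion.** The point holds in limited form. Two parts need no assumption about the task's composition. The derived score is not the proportion it is labelled as, under either reading of Trials. It also has no fixed chance level unless targets and non-targets are equal in number. It therefore mixes discrimination with willingness to press and ignores half of the recorded counts.

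The practical size is uncertain because the target share is not documented. For a sizeable shift towards caution under a signal-detection model, the effect is small at about 30–40% targets and large at 20% or 50%, with opposite signs at the two ends. The primary activation analysis and the sample size are untouched. This is a cheap improvement to a secondary, exploratory outcome. Its main value is to settle in advance which n-back measure is analysed and to let a memory change be told from a change in response style.

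**What to change.** **On the N-Back Task form.** Compute hit rate = hits/(hits + misses) and false-alarm rate = false alarms/(false alarms + correct rejections), and report both at each visit. State what a Trial is and how many targets and non-targets it contains. Keep the count score as a descriptive line only and drop the word Proportion from its label.

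**In Analysis Plans, Specific Aim #1.** Name one sensitivity index built from these rates as the n-back outcome. One option is d′ = z(hit rate) − z(false-alarm rate), adding 0.5 to each numerator and 1 to each denominator so that rates of 0 or 1 remain usable. Report the response criterion, −[z(hit rate) + z(false-alarm rate)]/2, beside it. Give the other index (here hit rate minus false-alarm rate) as a sensitivity analysis, since neither is free of response bias under every model. Interpret an n-back change as a memory change only if both indices agree.

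**Cost.** A small edit to one form and a short addition to the analysis plan. All four counts are already recorded, so data already collected can be rescored. The downside is slightly more analysis work and a score less familiar to readers than a count.
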